- 2) The percentage of patients that participate in NET and DBT-SUD skills. The dropout rate from the standard treatment, NET and DBT-SUD skills.
- The percentage of DBT-SUD skills sessions participated in, as well as the percentage of completed DBT homework.
- 4) A self-report questionnaire is designed to evaluate the experience of the treatment. Rating how different elements of the treatment are experienced on a 5-point scale. There are also open-ended questions about what is most and least helpful in the treatment.
- 5) The rate of destructive behaviour, such as suicidal behaviour, episodes of drug use and self-harm in the treatment period.

The secondary objective

- Evaluate the relationship between severity of substance abuse, destructive behaviours such
 as suicidal behaviour, self-harm and use of violence with experiences of traumatic events,
 PTSD symptoms severity, difficulties in emotion regulation, emotional avoidance, and
 experience of shame and guilt.
- 2) Evaluate the change from baseline to post-treatment, and at 3 and 12 months follow up, in PTSD symptom severity, depressive symptoms, difficulties in emotion regulation, emotion avoidance, and experience of shame and guilt.
- 3) Compare relapse rates at 3- and 12-months follow-up to previous rates at MBS.

Recruitment of participants:

All patients admitted to the inpatient program at Molde Treatment Center (MBS) from May 2021 to May 2024 will be invited to participate (N approx. = 100). All participants will participate in the standard treatment at MBS. Those who meet the inclusion criteria for further intervention will also be invited to participate in NET and/or DBT-SUD skills. Recruitment and follow-up plan is shown with patient flow chart in fig. 1.

Data collection

We will collect data: Five weeks after admission (T0), four weeks after completion of NET (T1), and at 3 months (T2) and 12 months (T3) follow up after discharge from MBS. An overview of measurements at each data collection point can be seen in table 1. For follow-up, patients will be contacted through telephone, nearest of kin, or social media. Follow-up will be conducted with an outpatient appointment or a home visit. Participation at 3- and 12-month follow will be rewarded with a gift card.

```

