*** Table 1****

**** Fig. 1****
```

All patients participating and all staff members working in the intervention period will be invited to answer a self-report questionnaire designed to assess the feasibility and acceptability of their experience with the treatment interventions (attachment 1 and 2).

General inclusion criteria for the study:

- 1) Fit general inclusion criteria for the in-patient program.
- 2) Speak Scandinavian (Norwegian, Danish and/or Swedish).
- 3) Be willing to sign the written informed consent.

General exclusion criteria for the study:

1) Have a clinically significant low cognitive- and/or linguistic functioning that hinders the patient in understanding and answering the questions on the self-report instruments.

Inclusion criteria for NET intervention:

- Experience of an aversive event that fits criteria A for PTSD as defined by Diagnostic and Statistical Manual of Mental Disorders-V (DSM-V) (American Psychiatric Association [APA], 2013).
- 2) Experience symptoms of PTSD as defined by the DSM-V (APA, 2013), or subthreshold PTSD (Grubaugh et al., 2005), or experience clinically relevant symptoms as evaluated by a NET therapist.
 - a. Subthreshold PTSD is defined as having experienced a traumatic event (Criteria A), meeting Criteria B (re-experiencing symptoms), Criteria E (one-month symptom duration), and Criteria F (significant distress or functioning impairment) and either Criteria C (avoidance or numbing symptoms) or Criteria D (hyper arousal symptoms).

Inclusion criteria for DBT intervention:

- 1) A history of pervasive difficulties in understanding and managing emotions as evaluated by an assigned DBT therapist.
- 2) Manage to commit to participating in the DBT- skills training.

Exclusion criteria for NET and/or DBT-SUD skills

- 1) Being actively psychotic.
- 2) Have a Body Mass Index (BMI) under 17.
- 3) Severe dissociation.
- 4) An ongoing traumatic contact with the perpetrator.

The intervention

The intervention period will be from May 2021- October 2024.

Molde Treatment Center (MBS)

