The institution is an inpatient, drug rehabilitation centre with room for 15 patients. The average treatment period is 6 to 9 months. Before admission, the patient usually has already been through the detox and abstinence phase. Patients are expected to be absent from substance use while in treatment at the facility. Standard treatment at MBS consists of a version of the therapeutic community (TC) a purposefully designed miniature drug-free social environment or residential treatment setting with clear rules to promote social and psychological change

(Vanderplasschen, Vandevelde, & Broekaert, 2014), family therapy (Hogue et.al, 2022), and CBT for SUD, that uses cognitive behavioural principles to manage drug addiction. CBT-SUD is delivered both individually and in-group settings (Otto et al., 2014).

Narrative exposure Therapy (NET) is a treatment for trauma disorders, particularly for individuals suffering from complex and multiple trauma (Elbert, Schauer, & Neuner, 2015). With the guidance of the therapist, a patient establishes a chronological narrative of his or her life, concentrating mainly on their traumatic experiences represented with stones, but also incorporating some positive events represented with flowers (Schauer, Neuner & Elbert, 2011). For patients who have themselves been offenders, we will add the narrative of violent/sexual offences represented by sticks as characterised in the further developed version of FORNET (Elbert et al., 2012). The therapy combines mapping, accepting and exposure to one's experiences. In the last session, a documented autobiographic narrative created by the therapist is presented to the patient.

The NET intervention consists of 10 - 18; 90-minute sessions with a NET therapist once or twice a week for 5 - 10 weeks.

- 1-2 sessions of introduction and psychoeducation on PTSD SUD and NET treatment.
- 1-2 sessions laying the lifeline.
- 3-15 sessions with working and writing the narrative, with the narrative repeated at the start of each session.
- 1 session where the complete narration is read and handed out in the last session.

 The patient often chooses to use the narration in family therapy sessions and share in treatment with a group of staff and fellow patients they themselves select.

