DBT-SUD skills is a group skills training component of Dialectical Behaviour therapy a comprehensive treatment focused on extensive difficulties in emotion regulation (Linehan, 1993). In this project, we will use a combination of the trans-diagnostic skill-training model by Neacsiu (Linehan, 2014; Neacsiu et. al., 2014) with an addition of SUD-specific skills. Every patient participating in the DBT skills training is assigned a DBT-trained therapist.

The DBT-SUD Skills intervention consists of:

- 2-3 sessions with a DBT therapist focusing on treatment orientation – mapping the patients' goals, obstacles, and resources, DBT- hierarchy, and commitment.

- Skills training 20, two-hour sessions twice a week over a period of 10 to 11 weeks. The skills consist of Mindfulness, Distress Tolerance, Interpersonal Effectiveness, Emotion regulation, and SUD-specific skills.
- Chain analysis in case of an episode of substance use or other dangerous destructive behaviour.
- One summary session with a focus on goals reached and troubleshooting.
- Support from DBT skills-oriented staff and environment.

Two DBT therapists lead the group, and each group consists of approx. 6-8 participants.

Patients start NET and DBT- SUD skills training one to two months after admission.

Measurement

Demographics. Basic demographic information from the participants is registered at admission. This includes age, gender, nationality, immigration status, level of education, employment/support status, living situation, marital status, children and custodianship, medical status, and legal status e.g. if the treatment is part of a criminal sentence. As well as questions regarding smoking or non-smoking and substance use cravings.

Substance use

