This study aims to develop and check the relevance, feasibility, acceptability and safety of adding to standard SUD inpatient treatment a combination of at trauma focused therapy (NET) and treatment for difficulties in emotion regulation (DBT- SUD - Skills). The aim is to measure the presence of trauma and trauma-related difficulties, assesses the pits and falls of the treatments, participation and its safety and potential benefits. Further the study makes it possible investigate the relationship between substance abuse, PTSD, difficulties in emotion regulation, emotional avoidance, shame, guilt and destructive behaviour such as suicide behaviour, self-harm and relapse into substance abuse.

Trial status

We are still open for recruitment, and the last participant is scheduled to be included by the start of May 2024. We plan for the last participant to complete treatment participation by end of October 2024. The data collection for the 3-month and 12-month follow-up will be completed by the end of October 2025.

Future research: If the intervention proves to be relevant, feasible, acceptable and safe, and of potential benefit for the patients, the future aim is to conduct a multicentre Randomized Control Trial (RCT) on the effect of combined NET and DBT-SUD skills integrated into SUD treatment.

Declarations

- *Ethics approval and consent to participate:* The Helsinki Declaration is followed and relevant permissions to the Regional Ethics Committee (REC) and Data Protection Services (DPS) is attained #203 428/2020. Informed consent was obtained from all individual participants included in the study.
- **Consent for publication:** Participants gave written consent for publication of all results not traceable to individual participant.

Availability of data end material: The data can be made available on request.

Competing interests: The authors declare that they have no conflict of interest.

Funding: This study was funded by the Department of Psychiatry, Møre og Romsdal Hospital Trust.

Author contributions: All authors contributed to the study conception and design. [name] and [name] perform material preparation, data collection and analysis. All authors contribute to the design of the study. [name] wrote the first draft of the manuscript and all authors commented on previous versions of the manuscript. All authors read and approved the final manuscript.

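### Does the projected October 2025 end of follow-up cut off 12-month visits for late-admitted, longer-stay patients?

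*Combined protocol and SAP*

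**What the plan says.** Trial status expects the final inclusion by the beginning of May 2024, the end of that participant's treatment participation by the end of October 2024, and then: "The data collection for the 3-month and 12-month follow-up will be completed by the end of October 2025". The Intervention section gives the same treatment horizon: "The intervention period will be from May 2021- October 2024".

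Data collection sets the visit timing. Baseline is "Five weeks after admission (T0"), and the follow-up visits are "at 3 months (T2) and 12 months (T3) follow up after discharge from MBS". On length of stay, the description of the centre says "The average treatment period is 6 to 9 months", in a "drug rehabilitation centre with room for 15 patients". On the added therapies: "Patients start NET and DBT- SUD skills training one to two months after admission".

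The 12-month data serve two secondary objectives: symptom change (objective 2) and relapse, "Compare relapse rates at 3- and 12-months follow-up to previous rates at MBS" (objective 3).

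**The concern.** The end date equals last inclusion plus 6 months plus 12 months, with no visit window. Because T3 runs from discharge, the schedule works for the last entrant only if the stay is near the bottom of the stated range. A longer stay puts T3 after the projected close.

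If contacts really stopped on that date, the patients without a 12-month visit would not be a random subset. They would be late admissions with long stays, while shorter-stay patients admitted in the same weeks would be fully observed. That would touch the 12-month relapse rate and the 12-month symptom change. Two terms also leave room for interpretation: inclusion (admission or baseline assessment) and the end of treatment participation (discharge or the end of NET/DBT). The Statistical analysis section gives no rule for missing visits.

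**Working it through.** **Inputs.** Last inclusion 1 May 2024 and projected close 31 October 2025 (Trial status); T3 at discharge + 12 months and baseline at admission + 5 weeks (Data collection); average stay 6 to 9 months and 15 places (description of the centre); recruitment over 36 months with N about 100 (Recruitment of participants).

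**The plan's own date.** 1 May 2024 + 6 months = 1 November 2024; + 12 months = 1 November 2025. This reproduces both October dates to within a day.

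**T3 due date for the last entrant, by length of stay.**

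| Stay (months) | Inclusion = admission on 1 May 2024 | Days past close | Inclusion = baseline (admitted 27 March 2024) | Days past close |
|---|---|---|---|---|
| 6 | 1 Nov 2025 | 1 | 27 Sep 2025 | -34 |
| 7 | 1 Dec 2025 | 31 | 27 Oct 2025 | -4 |
| 8 | 1 Jan 2026 | 62 | 27 Nov 2025 | 27 |
| 9 | 1 Feb 2026 | 93 | 27 Dec 2025 | 57 |

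The 3-month visit is safe throughout: with a 9-month stay from 1 May 2024 it falls on 1 May 2025.

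**Meaning of treatment participation.** If it means discharge, October 2024 + 12 months = October 2025, so the dates in Trial status agree with each other and imply a stay of about 6 to 7 months, inside the stated range. If it means NET/DBT, the latest skills training ends at 1 May 2024 + 2 months + 11 weeks = 16 September 2024. That also fits, but then October 2024 does not fix the discharge date.

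**Patients affected by a hard stop.** Assume even accrual over 36 months and no early dropout. If inclusion is admission, the share affected is (stay - 6)/36:
- 7.5 months: 1.5/36 = 4.2%
- 9 months: 3/36 = 8.3%

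If inclusion is baseline, 5 weeks (1.15 months) is gained, so the share is (stay - 7.15)/36:
- 7.5 months: 0.35/36 = 1.0%
- 9 months: 1.85/36 = 5.1%

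These shares should not be applied to N = 100. Fifteen places full for 36 months give 15 x 36 = 540 bed-months. A total of 100 patients therefore implies a mean stay of 540/100 = 5.4 months, at which T3 fits. Longer stays mean fewer patients: 540/7.5 = 72, or 540/9 = 60. The counts are then:
- Admission reading: 72 x 4.2% = 3 and 60 x 8.3% = 5
- Baseline reading: 72 x 1.0% = 0.7 and 60 x 5.1% = 3.1

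That is roughly 1 to 5 patients.

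**Effect on the 12-month relapse rate.** Shift = share missing x difference in relapse risk between missing and observed patients. The documents give no such difference, so 10 to 30 points is assumed. On the admission reading the shift runs from 0.042 x 10 = 0.4 points to 0.083 x 30 = 2.5 points. The 95% half-width at a rate of 50% is 1.96 x sqrt(0.25/n): 9.8 points at n = 100, 11.5 at n = 72 and 12.7 at n = 60.

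**The case for a change.** The strongest case for a change is that no reading of the dates accommodates an 8- or 9-month stay for the last entrant. The protocol was revised on 15 March 2024, weeks before recruitment closed, so this is its current schedule. Recruitment is defined by admission date, which favours the tighter reading. With no stated handling of visits due after the close, a team might drop them, or do them early and call them 12-month visits, which would shorten the period at risk of relapse. A few sentences would remove the doubt.

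The calendar arithmetic stands, and so does the ambiguity in the two terms. The step from a tight calendar to lost data does not. Trial status reports what the team expects; nothing in the text says that contacts end on a date. Timing T3 early would depart from Data collection, which ties the visit to discharge. The 6 to 9 months is an institutional average, neither a floor nor a ceiling for one patient, so it cannot contradict a 6- or 7-month expectation for the last entrant. One caveat: the flow chart (Fig. 1), cited as showing the follow-up plan, was not available for this check.

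**Conclusion.** This is a schedule without slack, not a contradiction, and no change to the plan is needed. The operative rule is that T3 falls 12 months after discharge. Following it means that a late, long-stay patient is seen after the projected date, and the projection slips by up to about three months for a 9-month stay.

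Even under a hard stop the loss is about 1 to 5 patients at one visit. The shift in a secondary, descriptive rate is at most about 2.5 points, well inside a half-width of about 10 to 13 points. Early dropout, which the study expects and measures, lowers the count further because early leavers reach T3 sooner; individual stays beyond 9 months would raise it. For symptom change, the mixed model still uses these patients' earlier scores. The primary objectives of relevance, feasibility, acceptability and safety do not depend on T3, and the protocol already concedes that without a randomised control group it cannot measure a direct effect.

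The sizes rest on even accrual, full beds, no early dropout and the assumed 10 to 30 point difference in relapse risk. The conclusion would differ only if data collection were in fact closed on the projected date and stays were much longer than the documents state.

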Fig. 1 Participant flow chart

Attachment 1 Translated version

Your experience of DBT-SUD skills training and NET, patient.

	Strongly				Strongly
	agree	Agree	Neutral	Disagree	disagree
How did you experience DBT-					
SUD skills training?					
Instructive	1	2	3	4	5
Useful for my problems	1	2	3	4	5
To difficult	1	2	3	4	5
Meaningsful	1	2	3	4	5
Helpful	1	2	3	4	5
Feasible	1	2	3	4	5
Relevant for my problems	1	2	3	4	5
How did you experience NET?					
Instructive	1	2	3	4	5
Useful for my problems	1	2	3	4	5
To difficult	1	2	3	4	5
Meaningsful	1	2	3	4	5
Helpful	1	2	3	4	5
Feasible	1	2	3	4	5
Relevant for my problems	1	2	3	4	5

What has been most helpful in the treatment?

What has been least helpful in the treatment?

Attachment 2

Translated versjon

Your experience of DBT-SUD skills and NET training, staff.

	Strongly				Strongly
	agree	Agree	Neutral	Disagree	disagree
How did you experience DBT-SUD skills training??					
Instructive for the patient	1	2	3	4	5
Useful for the patient	1	2	3	4	5
To difficult for the patient	1	2	3	4	5
Meaningsful for the patient	1	2	3	4	5
Helpful for the patient	1	2	3	4	5
Feasible for the patient	1	2	3	4	5
Feasble for the staff	1	2	3	4	5
Relevant for patient	1	2	3	4	5
Hvordan opplevde du					
behandlingen med NET?					
Instructive for the patient	1	2	3	4	5
Useful for the patient	1	2	3	4	5
To difficult for the patient	1	2	3	4	5
Meaningsful for the patient	1	2	3	4	5
Helpful for the patient	1	2	3	4	5
Feasible for the patient	1	2	3	4	5
Feasible for the staff	1	2	3	4	5
Relevant for patient	1	2	3	4	5

What has been most helpful in the treatment?

What has been least helpful in the treatment?
